3.4.1.1. Optional Expansion Cohort A3: Monotherapy

In addition, an optional expansion cohort of approximately 25 patients with aggressive lymphoma, including Richter's Transformation, DLBCL and MCL, can be enrolled simultaneously once activated. At least 15 patients in this cohort shall be MCL patients.

The optional expansion cohort A3 will be closed to accommodate testing two dose schedules in Cohort A2.

3.4.2. Expansion Cohorts B: Combination with Acalabrutinib

3.4.2.1. Expansion Cohort B2

Once the MTD/initial RP2D is established in Cohort B1 for MS-553 in combination with acalabrutinib, an expansion cohort will be opened. This cohort will evaluate MS-553 in combination with acalabrutinib in treatment experienced CLL/SLL patients who are BTK inhibitor naïve, are eligible for standard of care treatment with a BTK inhibitor as a single agent, and who have had no more than 2 previous lines of treatment regimens. Approximately 20 patients will be enrolled in Cohort B2 to further confirm the safety of the combination and assess early evidence of anti-tumor activity.

3.4.2.2. Expansion Cohort B3

Once the MTD/initial RP2D is established in Cohort B1, Cohort B3 will be opened in parallel to Cohort B2 to evaluate MS-553 in combination with acalabrutinib in treatment experienced CLL/SLL patients who are BTK inhibitor naïve, have TP53 abnormalities (including 17p deletion and P53 mutations), and have had no more than 2 previous lines of therapy. Once this cohort is open, all patients with TP53 abnormalities who are also naïve to BTK inhibitors will be preferentially enrolled in Cohort B3, rather than Expansion Cohorts B2. Approximately 10 treatment experienced CLL/SLL patients eligible for standard of care acalabrutinib will be enrolled in Cohort B3 to further confirm the safety of the combination and assess early evidence of anti-tumor activity.

3.4.3. Expansion Cohorts C: Combination of Venetoclax and Rituximab

3.4.3.1. Expansion Cohort C2

Once the MTD or initial RP2D is established in Cohort C1 for the combination of venetoclax, rituximab and MS-553, an expansion Cohort C2 will be initiated. Treatment experienced CLL/SLL patients who are eligible for standard of care venetoclax and rituximab, naïve to prior Bcl-2 inhibitor treatment and have had no more than 2 previous lines of treatment regimens can be enrolled. Approximately 20 patients will be enrolled to further confirm the safety of the combination and assess early evidence of anti-tumor activity.

3.5. Safety Review Committee

The SRC will monitor the safety of all patients in the dose escalation segment. The Committee will receive all available demographics, PK, and safety data (including, but not limited to, lab and ECG results, physical exam findings, vital signs, adverse events) for all patients dosed within a given cohort in order to make a decision regarding dose escalation to the next dose level. Based on the SRC's review, a dose escalation cohort may be expanded or an intermediate or a lower-than-planned dose level may be evaluated. The SRC will include the Sponsor representatives, the medical monitor, and Principal Investigators.

A separate Safety Management Plan outlines the roles and responsibilities for those involved in the collection and processing of Serious Adverse Events (SAEs), and pregnancies for this clinical study.

3.6. Remaining on Treatment

Patients will remain on treatment with MS-553 until disease progression, initiation of other anti-cancer therapy or investigational drug product, patient refusal of treatment or revocation of consent, or death due to any cause.

3.7. Response Assessment

Response data will be collected at screening and on day 1 of every cycle beginning with the first treatment visit and ending at the end of treatment visit, which should occur 30 (+ 7 days) after the last dose of study drug, if the condition of the patient permits, or up to the start of other anti-cancer therapy or investigational drug product(s), whichever is sooner. Patients who discontinue treatment for reasons other than progressive disease, use of other anticancer therapy or an investigational drug product, death, or withdrawal of consent will undergo response assessments every 12 weeks (± 7 days) until progressive disease occurs.

Response data consists of a combination of interviews, physical exams, labs, and scans. Not all labs and scans will be obtained at each time point. See Section 6.2 and Appendix 1 for complete details.

4. **PATIENT POPULATION**

CLL is most commonly a disease of the elderly, with a median age at diagnosis of 71, but disease has been witnessed in adults of all ages. This study is targeted at CLL adults of any age who meet the inclusion criteria for the cohort to which the patient is enrolled.

4.1. Inclusion Criteria

To be eligible for inclusion in the **dose escalation cohorts or expansion cohorts** in this study, patients must meet all of the following criteria:

- 1. Age 18 years or older.
- 2. Diagnosis of CLL or SLL:
 - a. History of histologically documented CLL or SLL that meets IWCLL diagnostic criteria according to the 2008 guidelines, and
 - b. Indication for treatment as defined by the 2008 IWCLL guidelines, or the need for disease reduction prior to allogeneic transplantation.
- 3. Cohort specific inclusion requirements:

Cohort A1 (MS-553 monotherapy)

Relapsed after, or is refractory to, progressing after at least two prior lines of therapies with the following exceptions:

- a. Patients with a 17p deletion who have already received venetoclax; or
- b. Patients who have *TP53* mutation (prior therapy is not required) which shall be confirmed at screening for enrollment.

- c. Patients with clinical and/ or molecular (e.g., BTK and/or PLCG2 mutation) resistance after achieving initial response to a BTK inhibitor.
 - For patients without clinical resistance, molecular resistance (i.e., BTK and/or PLCG2 mutation) shall be confirmed at screening for enrollment.

Cohort A2 (MS-553 monotherapy)

Relapsed/refractory CLL/SLL patients who have:

a. Failed at least two prior lines of therapies, or

- b. Developed clinical and/or molecular (i.e., BTK and/or PLCG2 mutation) resistance after achieving an initial response to a BTK inhibitor
 - For patients without clinical resistance, molecular resistance (i.e., BTK and/or PLCG2 mutation) shall be confirmed at screening for enrollment.

Cohort A3 (MS-553 monotherapy) See Inclusion Criterion #4 below

Cohort B1, B2 (MS-553 in combination with acalabrutinib)

Treatment experienced patients with no more than two prior lines of therapies, who

- a. Are naïve to prior BTK inhibitor treatments, and
- b. Are eligible for single agent BTK inhibitor

Cohort B3 (MS-553 in combination with acalabrutinib)

Treatment experienced patients with no more than two prior lines of therapies, who

- a. Are naïve to prior BTK inhibitor treatments, and
- b. Are eligible for single agent BTK inhibitor, and
- c. Have 17p deletion or TP53 mutation which shall be confirmed screening for enrollment.

at

Cohort C1, C2 (triplet regimen of MS-553 + rituximab + venetoclax)

Treatment experienced patients receiving no more than 2 prior lines of treatment regimens, who

- a. Are naïve to prior Bcl-2 inhibitor treatments, and
- b. Are eligible for venetoclax in combination with rituximab.
- 4. For inclusion in the Cohort A3, patients must meet both of the following diagnostic criteria *instead of* inclusion criterion #2or #3:
 - a. Diagnosis of aggressive lymphoma, explicitly comprising Richter's Transformation of CLL/SLL to Diffuse Large B-Cell Lymphoma (DLBCL); Activated B-cell (ABC), or non-GCB DLBCL not transformed from CLL/SLL, or MCL. Other histologies may be included after discussion with and approval of the study principal investigator and Sponsor medical monitor.
 - b. Additionally, patients with MCL or de novo ABC or non-GCB subtype DLBCL patients must have received at least two lines of prior therapy and MCL patients must have failed at least a BTK inhibitor. Patients with Richter's transformation have no such restriction on the use of prior therapy.
- 5. WHO/ECOG performance status ≤ 2 .

- 6. Meet laboratory parameters (see Exclusion Criteria).
- 7. In the opinion of the investigator, all of the following criteria are met:
 - a. Have life expectancy \geq 2 months
 - b. Are willing to undergo all study-related evaluations and procedures, and
 - c. Have ability to understand and willingness to execute a written informed consent document.

4.2. Exclusion Criteria

Patients who meet any of the following criteria are not eligible for this study.

- 1. Current transformation of CLL/SLL to PLL, non-Hodgkin lymphoma, or Hodgkin lymphoma.
 - d. Patients being considered for inclusion in the optional expansion cohort (aggressive lymphoma) are not excluded on the basis of transformed lymphoma but must meet the definition of aggressive lymphoma outlined in the inclusion criteria for Cohort A3.
- 2. Active and uncontrolled autoimmune cytopenia(s).
- 3. Any of the following prior therapies within 14 days prior to Cycle 1 Day 1:
 - a. Major surgery
 - b. Corticosteroids greater than 20 mg / day prednisone (or equivalent), unless used by inhalation or topical route, or unless necessary for premedication before and/ or after iodinated contrast dye. Higher doses, and more prolonged courses of steroids are permitted under certain circumstances after discussion with the medical monitor and/or Sponsor including, but not limited to, the following:
 - i. Treatment of disease-related autoimmune hemolysis or autoimmune thrombocytopenia;
 - ii. Symptomatic relief of lymphadenopathy preferably after completion of Cycle 1;
 - iii. Symptomatic relief of B symptoms after completion of Cycle 1;
 - iv. Treatment of GVHD please discuss with medical monitor;
 - v. Short courses (up to 14 days) if needed for any intercurrent condition such as acute exacerbation of any non-disease-related condition (e.g., arthritis, asthma, COPD) including steroid dose modification required for adrenal insufficiency.
 - c. Cytotoxic chemotherapy or biologic therapy, with the exception of BCR pathway kinase inhibitors for which only a 24-hour wash out prior to Cycle 1 Day 1 is required.
- 4. Failure to recover:

- a. From toxicity to Grade 1 or less from prior chemo- or radiotherapy or biologic therapy with the exception of alopecia, atrial fibrillation or hypertension that developed during treatment with a BTK inhibitor.
- b. To Grade 2 or less for atrial fibrillation or hypertension that occurred as a consequence of treatment with a BTK inhibitor.
- 5. CNS leukemia/lymphoma including history of treated CNS disease even if the patient is asymptomatic.
- 6. Inadequate bone marrow function / hematopoietic reserve, except in the case of documented bone-marrow involvement, evidenced as:
 - a. Absolute Neutrophil Count (ANC) < 1×10^9 /L
 - b. Platelet count < 30×10^9 /L
- 7. Inadequate liver or renal function as specified below:
 - a. Serum total bilirubin > 2 x ULN (upper limit of normal), or > 3 x ULN in case of liver involvement with CLL/SLL, or serum total bilirubin > 3 x ULN in patients with documented history of Gilbert's disease and normal direct bilirubin.
 - b. AST or ALT > 2.5 x ULN, or > 5 x ULN if CLL/SLL is present in the liver.
 - c. Estimated GFR < 30 mL/min.
- For Cohort B patients, active treatment with strong CYP3A inhibitors, CYP3A inducers or proton pump inhibitors, unless medication can be stopped prior to enrollment in the study.
- For Cohort C patients, active treatment with strong and moderate CYP3A inhibitors, strong CYP3A inducers, or strong P-gp inhibitors unless medication can be stopped prior to enrollment in the study.

- 12. Receiving treatment with medications that are known to be strong inducers, inhibitors or sensitive substrates of CYP3A4/5 or medications with risk for QT prolongation that cannot be discontinued prior to study entry (at least 48 hours prior to the start of Cycle Day 1 dosing). For any exceptions, discussion with medical monitor and/or Sponsor is needed. Weak or moderate inhibitors may be used with caution, except as otherwise specified in Exclusion Criteria. Examples of these medications are listed in Appendix 3.
- 13. Clinically significant cardiac diseases, including any of the following:
 - a. History or presence of ventricular tachyarrhythmia

- b. Presence of unstable/uncontrolled atrial fibrillation is exclusionary. Patients with stable atrial fibrillation (rate controlled pharmacologically) are eligible provided that they do not meet any other exclusion criteria. Patients whose atrial fibrillation occurred as a consequence of treatment with a BTK inhibitor may be eligible for the study provided that the patient is asymptomatic and on a stable dose of medication for rate control, and only after discussion with the medical monitor.
- c. Unstable angina pectoris or acute myocardial infarction within 3 months prior to start of study drug.
- d. NYHA functional class III or IV heart failure
- e. Baseline QTcF interval of > 480 msec. Prior QTc prolongation due to prior medication no longer on board is not exclusionary. A family history of QTc interval prolongation by itself is not exclusionary provided that the patient's QTc is not prolonged. For those with prolonged QTc interval due to bundle branch block, patient may be eligible after documentation of a "corrected value" ≤480 msec and confirmation by cardiologist that patient is asymptomatic and that no other cardiac conduction or cardiac abnormality is present that would pose any safety issue for the patient.

Note: As the eligibility criteria specify the QT interval corrected by the method of Fridericia (QTcF), any correction for widened QRS should be sure to include a cuberoot corrected R-R interval. Please discuss/consult with a cardiologist if there are any questions.

- 14. History of another malignancy that in the opinion of the investigator limits survival to less than 2 years.
- 17. Gastrointestinal dysfunction, including motility or malabsorption syndromes or inflammatory bowel disease which could limit absorption of MS-553.
- 18. Known HIV positivity, or active hepatitis B or C infection with detectible viral nucleic acid in the blood.
- 19. Severe systemic infections requiring intravenous antibiotics within the two weeks prior to initiation of MS-553.
- 20. Any other life-threatening illness, medical condition, or laboratory abnormalities or therapies that in the opinion of the investigator could compromise the safety of the patient or interfere with analysis of study endpoints.
- 21. Women who are lactating or pregnant.
- 22. Women of child-bearing potential or male partners of women of child-bearing potential who will not agree to use highly effective method of contraception throughout the entire

study period and for a minimum of 3 months after the last dose of study drug. Highly effective contraception methods include:

- a. Total abstinence or
- b. Male or female sterilization or
- c. Combination of any two of the following:
 - i. Use of oral, injected or implanted hormonal methods of contraception
 - ii. Placement of an intrauterine device (IUD) or intrauterine system (IUS)
 - Barrier methods of contraception: condom or occlusive cap (diaphragm or cervical/vault caps) with spermicidal foam/gel/film/cream/vaginal suppository.

Women are considered post-menopausal and not of child-bearing potential if they have had 12 months of natural (spontaneous) amenorrhea with an appropriate clinical profile (age appropriate, history of vasomotor symptoms) or have had surgical bilateral oophorectomy (with or without hysterectomy) or tubal ligation at least six weeks ago. In the case of oophorectomy alone, only when the reproductive status of the woman has been confirmed by follow up hormone level assessment is she considered not of childbearing potential.

Women of child-bearing potential who will not agree to the following are ineligible for the study:

- Refrain from breastfeeding and donating oocytes or blood during the course of the study and for 3 months after the last dose of study medication, and
- Ongoing pregnancy testing during the course of the study and at the end of treatment visit.
- 23. Men who will not agree to the following are ineligible for the study:
 - Refrain from donation of sperm or blood during the course of the study and for 3 months after the last dose of study medication, **and**
 - Completely abstain from sexual contact, or must always use a latex or synthetic condom during any sexual contact until 3 months after the last dose of study drug, or have prior documentation of surgical sterilization.

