6.1.2. Screening Period

Screening procedures shall be performed within 28 days prior to first dose of study drug unless otherwise stated. Procedures may be conducted over multiple visits if necessary.

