6.1.11. Visit Schedule

The schedule of visits including which study related procedures are to be performed and which samples are to be collected at each time point is described graphically in Appendix 1A (A Cohorts), 1B (B Cohorts), and 1C (C Cohorts).

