7.9. Pregnancy

Pregnancy is an exclusion criterion. All patients should be instructed to immediately notify the investigator and study staff of pregnancy that occurs during the study period. Any female patient who becomes pregnant should immediately discontinue the study medication. Although pregnancy itself is not an AE, if a study patient or the partner of a study patient should become pregnant during the course of the study this should be reported on a pregnancy report form and the pregnancy should be followed to conclusion with the outcome(s) including any untoward events in mother or child reported to the study Sponsor.

[figure not shown]

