APPENDIX 1A: STUDY CALENDAR A COHORTS (MS-553 MONOTHERAPY)

Visit Evaluation Schedule

Study Cycle (28 days)	0		1	2	3	4+		EOT ^a	S/RFU ^b
Cycle day ⁱ	Screening ^h	1	8	1 (± 3 days)	1 (±3 days)	1 (±3 days)		±7 days	Q12 wks ±7d for response or Q24
Study Procedure/Assessment									wks ±7d for survival
	Study Drug Disp	pensatior	ı				ntil disease progression, toxicity, or other withdrawal		
MS-553 PO BID		х		х	х	х	thdr		
	Procedu	res					er wi		
Informed Consent	×						othe		
Confirmation of inclusion/exclusion criteria	х						y, or		
Demographics	х						xicit		
Medical History and Physical Exam	х	х	х	х	х	х	n, to	х	х
Concomitant medication survey	х	х	х	х	х	х	ssio	х	
Adverse Events Assessment ^p		х	х	х	х	х	ogre	х	
Vital signs; height ^k /weight	х	х	х	х	х	х	se pi	х	х
WHO/ECOG Performance Status	х	х	х	х	х	х	lisea	х	х
Electrocardiogram	х	х	х	х			ntil c		
	Laboratory S	Studies					-wollo		
Complete blood count with differential	х	х	х	х	х	x	Continuin	х	х
Serum chemistry ^e	х	х	х	х	х	x	Cont	х	
Urinalysis	х						-		

Study Cycle (28 days)	0		1	2	3	4+		EOT ^a	S/RFU ^b
Cycle day ⁱ	Screening ^h	1	8	1 (± 3 days)	1 (±3 days)	1 (±3 days)		±7 days	Q12 wks ±7d for response or Q24
Study Procedure/Assessment									wks ±7d for survival
Urine pregnancy test ^f	Х								
HIV Ab, Hepatitis C Ab, HBsAg, anti-HBcAb	х								
Interphase FISH and stimulated cytogenetics ⁰	х								
IGHV mutation status	х								
Flow Cytometry ^o	х			See no	ote l			See note l	
	Radiographic	Studies							
CT scans ^g	Х					x ^g			х
Ex	oloratory (Correl	ative) Stu	ıdies						
Pharmacokinetic samples	See Section 6.2.3 and Table 7								
								See Section	
Correlative sciences samples		See Section 6.3.2 and Table 8							
								Table 8	

Footnotes:

- a. EOT (End of Therapy) visit; should occur 30 ± 7 days after last dose of study drug or prior to the start of a new anticancer therapy, whichever is sooner.

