- b. S/RFU (Safety/Response Follow Up); Patients who discontinue treatment for progressive disease and/or use of other CLL/SLL therapy will be followed for survival every 24 weeks (± 7 days) for up to 3 years. Patients who discontinue treatment for reasons other than progressive disease, use of other CLL/SLL therapy, death, or withdrawal of consent will have response assessments every 12 weeks (± 7 days) until progressive disease occurs. Thereafter they will be followed for survival every 24 weeks (± 7 days) for up to 3 years. All patients will discontinue survival follow-up upon completion of 3 years of survival follow-up, withdrawal of consent, death, or study closure, whichever is the earliest. For assessment of survival, only a review of patient chart and/or a phone call is required.
- c. 100, 200, 250, 300 mg or intermediate doses PO BID according to dose level. Study staff should record clinic-administered doses in the dosing diary and patient should record home doses in the dosing diary.
- e. Serum chemistry should include albumin, alkaline phosphatase, AST, ALT, bicarbonate, BUN, calcium, creatinine, glucose, LDH, magnesium, phosphate, potassium, sodium, total bilirubin, total protein, and uric acid.
- f. A urine pregnancy test should be performed with screening in every woman of childbearing potential prior to study entry.
- g. In the CLL/SLL cohorts, CT scans of the chest, abdomen, and pelvis (and neck if involved) should occur at screening and at the post 3, post 6, and post 9 cycles of therapy assessments (i.e., at or prior to Cycle 4 Day 1, Cycle 7 Day 1, and Cycle 10 Day 1). Patients who continue with drug therapy after 9 cycles

of treatment should have CT scans, preferably every 12 weeks, or as clinically indicated until disease progression. In the aggressive lymphoma cohort, CT scans of the chest, abdomen, and pelvis (and neck if involved) should occur at screening and as clinically indicated or at a minimum of every 24 weeks while on treatment. Other image tools for response assessment may be used per RECIL 2017 for lymphomas.

- h. Screening procedures shall be performed within 28 days prior to first dose of study drug. Studies performed at the study site prior to patient signing of informed consent can be utilized for screening purposes if obtained within 28 days before first dose of study drug, except in the case of *IGHV* mutation status which are permitted to have been obtained at any time prior to screening.

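### Criterion 22 requires agreement to ongoing and end-of-treatment pregnancy testing, but all three study calendars schedule a urine pregnancy test at screening only

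*Combined protocol and SAP*

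**What the plan says.** Criterion 22 in Section 4.2 opens its list of conditions with "Women of child-bearing potential who will not agree to the following are ineligible for the study", and one of those conditions is "Ongoing pregnancy testing during the course of the study and at the end of treatment visit". The synopsis carries the same condition. It has two parts: testing repeated during the study, and a test at a named visit, end of treatment (EOT).

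The three calendars each have a urine pregnancy test row with one mark, under Screening. Footnote f is the same in all three: "A urine pregnancy test should be performed with screening in every woman of childbearing potential prior to study entry".

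Section 6.1.11 gives the calendars their standing. It says they set out "The schedule of visits including which study related procedures are to be performed and which samples are to be collected at each time point". Section 6.1.2 fixes the screening window: "Screening procedures shall be performed within 28 days prior to first dose of study drug unless otherwise stated". Section 7.9 says what follows if a patient conceives, "Any female patient who becomes pregnant should immediately discontinue the study medication", and relies on notification: "All patients should be instructed to immediately notify the investigator and study staff of pregnancy that occurs during the study period". It sets no test.

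**The concern.** The eligibility text and the calendars describe different amounts of testing. A patient is asked to accept repeated and end-of-treatment tests as a condition of entry, and the schedule that sites work from contains neither. Sites usually build visit worksheets and orders from the calendar, so the likely result is that the testing is left out, or is done at intervals that differ between sites.

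What is at stake is patient safety rather than an analysis. Section 7.9 calls for study drug to stop at once on pregnancy, and treatment may continue for as long as the patient tolerates the drug and has not progressed. A rule that depends on knowing about a pregnancy is weaker when the testing meant to support it is not scheduled.

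**Working it through.** The plan gives no figure to reproduce, and the only arithmetic is a count. The check sets the eligibility condition beside the pregnancy-test row of each calendar.

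| Source | Screening | On treatment | EOT |
|---|---|---|---|
| Criterion 22 (Section 4.2, synopsis) | not addressed | required, no interval given | required |
| Appendix 1A, row and footnote f | 1 test | 0 | 0 |
| Appendix 1B, row and footnote f | 1 test | 0 | 0 |
| Appendix 1C, row and footnote f | 1 test | 0 | 0 |

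Calendars with an on-treatment test: 0 of 3. Calendars with an EOT test: 0 of 3.

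**Could the missing marks be a conversion fault?** This is unlikely. In the same tables, the complete blood count and serum chemistry rows keep their marks in the treatment-cycle and EOT columns. Footnote f is legible in all three appendices and agrees with the single mark.

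**Is the testing placed somewhere else?** I found it in none of the readable sections.

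- The serum chemistry panel (footnote e of each calendar) lists no pregnancy marker.
- Section 6.2.1, on safety assessments, lists laboratory tests, vital signs, ECGs and physical condition, and no pregnancy test.
- Section 6.1.12 lists the mandatory visits but attaches no test to them.
- Section 7.9 deals with a pregnancy once it is known and gives no schedule for finding one.

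**Which text would a site follow?** Section 6 and Section 6.1.11 both refer sites to Appendix 1 for procedures by visit. Criterion 22 gives no interval, so even a site that noticed the condition could not tell how often to test during treatment. Only the EOT visit is named.

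**The case against.** Several points on the other side stand, and they limit how far the conclusion goes.

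**Criterion 22 is itself protocol text.** Strictly, it asks for agreement to testing. A site reading the whole protocol has notice of the EOT test and may also test under local practice. So the conclusion is about a site that follows the calendars as written, not about every site.

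**A reader might infer that the lack of a test on Cycle 1 Day 1 is also a contradiction**, because the screening result may be up to 28 days old at first dose. The documents do not support that. Criterion 22 names no pre-dose test, and Section 6.1.2 and footnote f agree with each other. The age of the result is a fair question for the sponsor, but no two passages conflict on it.

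**A reader might infer that a pregnancy on treatment could not be detected except by self-report.** That is too strong. All three calendars schedule history and physical examination at the Day 1 visits and at EOT. These do not replace a test, but they are contacts at which a pregnancy could come to light. Section 6.1.8 does say that the effect of MS-553 on hormonal contraceptives is unknown, but the same sentence responds by requiring at least two methods of contraception.

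**A reader might put a duration on the gap** by taking 24 cycles × 28 days = 672 days. In Section 6.2.2, 24 cycles is a checkpoint for patients with stable disease and no response by 9 cycles. It is not an expected treatment duration, and Section 3.2 says the median duration is unknown. The figure adds nothing to the count of zero.

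**Some material cannot be seen.** Section 9.3 treats the consent form as part of the protocol, and consent pages are not in the public document. Some calendar footnotes are missing, and at least one row marker has been lost (the ECG row in Appendix 1A shows no marker although footnote j governs it). A schedule given elsewhere cannot be ruled out. That would not cure the calendars, whose row and legible footnote f are screening-only.

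**Conclusion.** The inconsistency is real. The on-treatment and EOT testing in criterion 22 has no matching entry in Appendix 1A, 1B or 1C: 0 of 3 calendars on each count. A site following the calendars as written would not carry out the testing to which the patient had to agree.

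The practical size is modest. The documents do not say how many women of child-bearing potential are expected. Section 4 gives a median age at CLL diagnosis of 71 but admits adults of any age, so the number is probably small and not zero. No endpoint, analysis population or estimate is affected. The point should be corrected because it concerns a safety procedure that the protocol itself names.

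This rests on two assumptions: that the empty cells are genuine, which the intact neighbouring rows and footnote f support, and that no unseen text overrides the calendars. The conclusion does not extend to a missing pre-dose test or to a claim that pregnancies would go undetected.

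**What to change.** Reconcile criterion 22 with the three calendars:

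1. The sponsor states the on-treatment testing interval that criterion 22 leaves open.
2. In Appendices 1A, 1B and 1C, enter that interval and the EOT test in the pregnancy-test row, for women of child-bearing potential.
3. Amend footnote f in each appendix to match, and check that the synopsis, Section 4.2 and the consent form agree.

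If the sponsor intends screening-only testing, criterion 22 and the synopsis should be changed instead, with the reason given. Whether to repeat the test before the first dose, given the 28-day window, is a separate decision for the sponsor and should be recorded either way.

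The cost is one row and one footnote in each of three calendars. If the on-treatment interval is set to fall on visits already in the calendar, as EOT does, the only further cost is a urine test in a small subset of patients, with no extra visits.
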